8. ANALYSIS POPULATIONS

Protocol violations/deviation will be defined prior to data-base lock and statistical analysis. Applicability of patient to ITT and PP population will be reviewed by sponsor's medical expert.

8.1 INTENT-TO-TREAT POPULATION

The Intent-to-treat (ITT) population will include all randomized patients who receive at

least one dose of study medication and have at least one post-baseline¹ efficacy measurement; it will be based on the treatment randomized, regardless of the treatment actually received. The ITT will be used for all efficacy analyses. Subject will be summarized according to the treatment to which they were randomized.

8.2 POPULATION PER PROTOCOL

ITT population patients comply with the per-protocol population if they complete the study treatment period, have all assessments for the primary efficacy analysis and considered compliant. The patients are compliant if they do not have any major protocol violations in the course of the study.

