3.2 STUDY TREATMENT

The patients will be assigned to one of two treatment group in 1:1 ratio:

- Group 1. OKITASK® 40 mg – 35 patients
- Group 2. Placebo – 35 patients

The patient will assess pain by VAS at 0' – immediately before study drug dosing.

Upon study drug administration the patients will immediately start two stopwatches. One of them will be stopped once the patient feels first perceptible pain relief; the second one will be stopped once the patient feels the meaningful pain relief.

The patient will stay at the site for 6 hours post-dose for pain and AE assessment. Pain intensity will be assessed by VAS at 5', 10', 15', 30', 45', 60' (1 hour), 90' (1.5 hours), 120' (2 hours), 180' (3 hours), 240' (4 hours), 300' (5 hours), and 360' (6 hours) post-dose.

Pain relief will be assessed by VAS at 5', 10', 15', 30', 45', 60' (1 hour), 90' (1.5 hours), 120' (2 hours), 180' (3 hours), 240' (4 hours), 300' (5 hours), and 360' (6 hours) post-dose.

Patients should mark actual time points of VAS measurement. Deviations from planned time points will not be considered as protocol deviations. Only omitted values will be considered as protocol deviations.

Patients' overall assessment will be performed right before the discharge from the site.

Follow-up phone call to the patient to assess AEs will be performed on Day 3 (48 hours

after the study drug dosing). Any SAE spontaneously reported by the patient within 30 days of dosing will be collected.

Should the patient require rescue medication at any time during 6 hours post-dose, the last VAS measurement and patient's overall assessment will be performed before the rescue medication dosing.

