4. CONCOMITANT MEDICATION

All concomitant medications, including herbal therapy and biologically active supplements (BAS) must be registered in the source documentation and on the eCRF. This includes all pharmaceutical products and BAS.

The concomitant therapy also includes anesthesia and rescue therapy allowed by the protocol which is applied to relief pain (if applicable).

Ultracain D (articaine 40 mg), Ultracain DS forte (articaine+epinephrine 40 mg+0.01 mg/ml), Ultracain DS (articaine+epinephrine 40 mg+0.005 mg/ml) 1-2 capsules can be used for anesthesia. The Investigator can choose anesthesia taking into consideration the patient's condition, medical history and other reasons. Number of used capsules and type of anesthesia for each patient will be recorded in the source documentation and on the eCRF.

In the event of poor pain control, the patient will receive a rescue medication for analgesia (i.e. Paracetamol 500-1000 mg tablets). Subjects will be encouraged to postpone the rescue medication until after 1-hour post-dose. If Paracetamol 500-1000 mg is not effective, the patient will be allowed to take another dose of Paracetamol 500-1000 mg every 6-8 hours; interval between dose taking is not less than 4 hours; the maximum daily dose is 4000 mg.

The drug name (preferably the name of the active substance), dosage, frequency of administration, route of administration, indication for use (including the underlying disease, comorbid conditions, adverse event, or prevention), the date of beginning and ending of a concomitant drug administration should be registered in the source

documentation and on the electronic Case Report Form.

If by the time of the study completion the concomitant therapy continues, a corresponding mark shall be entered on the electronic Case Report Form.

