10. EFFICACY AND SAFETY ASSESSMENT

Efficacy parameters will be assessed for the ITT population. Primary efficacy variable also be assessed for the PP population.

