10.1 PRIMARY EFFICACY VARIABLE

Primary variable will be the AUC_{0-6h} without or with LOCF of pain intensity profile between time 0 (baseline value of VAS) and 6 hours post-treatment. AUC_{0-6h} analysis will be based on **actual rather than scheduled timings** and will be calculated using the trapezoidal rule:

$$\sum \frac{P_n + P_{n-1}}{2} (t_n - t_{n-1})$$

where, P_n – pain intensity at point n, t_n – time point n.

Treatment AUCs will be compared using ANOVA methodology (simple GLM model). In case of significant covariates discovered during baseline data analysis, such covariates could be added to the ANOVA model (level to stay 0.15). F-test for type III treatment effect will be used for testing the Null hypothesis.

Null hypothesis (H_0) that OKITASK® is no different from Placebo will be rejected and alternative hypothesis (H_1) that OKITASK® is superior to Placebo will be accepted if mean AUC_{0-6h} (OKITASK®) is less than mean AUC_{0-6h} (Placebo) and $p < 0.05$.

$$H_0: \mu_T = \mu_R$$

$$H_1: \mu_T \neq \mu_R$$

where μ_T – OKITASK® (**Test**) mean AUC_{0-6h} ; μ_R – Placebo (**Reference**) mean AUC_{0-6h} .

If the actual time is not recorded, the scheduled time will be used instead. LOCF approach will be applied as described in Section 7.

Additional test on FCS replaced data will be performed to confirm analysis of the LOCF data (sensitivity).

For the PP population data could not be missing. There were no LOCF or other methods applied.

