12. TABLE EXAMPLES¹

Table 12.1 Disposition

	OKITASK® N = XX	PLACEBO N = XX
Screened		xx
Safety population	xx (xx.x%)	xx (xx.x%)
Intent-to-treat (ITT) population	xx (xx.x%)	xx (xx.x%)
Per-Protocol (PP) population	xx (xx.x%)	xx (xx.x%)
Study completion	xx (xx.x%)	xx (xx.x%)
Early termination	xx (xx.x%)	xx (xx.x%)
Adverse event	xx (xx.x%)	xx (xx.x%)
Death	xx (xx.x%)	xx (xx.x%)
Patient required rescue medication	xx (xx.x%)	xx (xx.x%)
Lost to follow-up	xx (xx.x%)	xx (xx.x%)
Consent withdrawn	xx (xx.x%)	xx (xx.x%)
Investigator decision	xx (xx.x%)	xx (xx.x%)
Protocol violation, including non-compliance	xx (xx.x%)	xx (xx.x%)
Patient required prohibited medications		
Protocol entry criteria not met	xx (xx.x%)	xx (xx.x%)
The patient starts of another study drug	xx (xx.x%)	xx (xx.x%)
Study is stopped by Sponsor decision	xx (xx.x%)	xx (xx.x%)
Study is stopped by regulatory instance / ethics committee	xx (xx.x%)	xx (xx.x%)
Pregnancy	xx (xx.x%)	xx (xx.x%)
Other	xx (xx.x%)	xx (xx.x%)

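### The per-protocol set excludes compliant patients who take the permitted rescue before 6 hours, so membership depends on outcome, and the ITT LOCF analysis shares most of that selection

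*SAP*

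**What the plan says.** - **PP definition (SAP 8.2).** ITT patients enter PP "if they complete the study treatment period, have all assessments for the primary efficacy analysis and considered compliant". Compliance, meaning no major violation, is only the third of three conditions.
- **PP data (SAP 10.1).** "For the PP population data could not be missing", and neither LOCF nor any other replacement is used there.
- **Rescue is permitted (SAP 4).** "In the event of poor pain control, the patient will receive a rescue medication for analgesia". Patients are only encouraged to wait one hour.
- **VAS recording ends at rescue (SAP 3.2; Table 3.1, note 1).** If rescue is needed within 6 hours, "the last VAS measurement and patient's overall assessment will be performed before the rescue medication dosing".
- **Rescue counts as non-completion (SAP Table 12.1).** "Patient required rescue medication" is a reason line under early termination. Protocol violation has its own line.
- **Role of PP (SAP 10).** "Primary efficacy variable also be assessed for the PP population". The results go into Tables 12.10 and 12.12.
- **Endpoint window (SAP 10.1).** The AUC covers the "pain intensity profile between time 0 (baseline value of VAS) and 6 hours post-treatment".

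**The concern.** A PP analysis is meant to show the treatment effect in patients who followed the protocol. Here a patient can follow it exactly, take rescue that the plan allows, and still be excluded, because the period was not completed and later readings do not exist. The excluding event is inadequate pain control. It occurs after randomisation, and the SAP itself compares it between arms as a secondary objective (5.2). If rescue is commoner on placebo, PP loses more of its worst placebo outcomes than of its worst active ones. The arms are then no longer comparable by randomisation, and they shrink unequally.

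**Working it through.** **Step 1: follow one patient through the text.** A patient with no violation is rescued at, say, 3.5 h.
- 3.2: the last VAS is taken before the rescue dose, so there are no readings at 4, 5 and 6 h.
- Table 12.1: the patient is an early termination, so the completion condition of 8.2 fails.
- 8.2: not all primary assessments are present, so the second condition fails too.
- 10.1: no replacement is allowed in PP, so nothing brings the patient back.
- Section 8: the sponsor's medical expert reviews membership, but no exception for rescue is written.

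**Step 2: does ITT compensate?** Section 7.1 says that when no observed value follows two missing ones, nothing is replaced and the data are invalid. The last case of Table 7.1, with three trailing gaps, shows this. Rescue before the 5 h reading leaves at least the 5 h and 6 h values missing, so the ITT LOCF AUC is lost as well. Essentially only rescue between the 5 h and 6 h readings (one trailing gap) leaves a patient in ITT LOCF but out of PP.

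**Step 3: reproduce the plan's sample size (SAP 6).** Two-sided normal approximation:

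n = 2 × 121² × (1.960 + 0.842)² / 90² = 28.4, so 29 per arm and 58 in total, as stated.

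29 / 0.85 = 34.1, so 35 per arm and 70 in total, as stated. An arm of 35 falls below 29 once more than 1 − 29/35 = 17% leave.

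**Step 4: size of the selection.** The SAP gives no rescue rate, so the rescue models here are assumptions. Inputs from SAP 6: placebo AUC N(263, 106), ketoprofen N(173, 121), planned difference 90. Normality is assumed.

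If everyone with AUC above a cut c is rescued, then with a = (c − μ)/σ the share retained is Φ(a) and the mean of those retained is μ − σφ(a)/Φ(a).

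Cut 360 (mean pain 60 mm over 6 h):
- Placebo: a = 0.915, Φ = 0.820, mean = 263 − 106 × 0.2625/0.820 = 229.1
- Active: a = 1.545, Φ = 0.939, mean = 173 − 121 × 0.1209/0.939 = 157.4
- Difference: about 72

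Cut 300 (mean pain 50 mm):
- Placebo: a = 0.349, Φ = 0.637, mean = 263 − 106 × 0.3754/0.637 = 200.5
- Active: a = 1.050, Φ = 0.853, mean = 173 − 121 × 0.2300/0.853 = 140.4
- Difference: about 60, with about 22 and 30 of 35 patients left

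For looser links, the probability of rescue is logistic in AUC (midpoint/scale):

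| Rescue model | Placebo leaving | Active leaving | PP difference |
|---|---|---|---|
| Cut 300 | 36% | 15% | 60 |
| Cut 360 | 18% | 6% | 72 |
| Logistic 300/60 | 40% | 21% | 74 to 75 |
| Logistic 360/60 | 26% | 12% | 78 |
| Logistic 360/120 | 33% | 21% | 85 |
| Logistic 300/150 | 45% | 32% | 88 |

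A second set of models fixes the placebo rescue rate and applies one threshold to both arms. With rescue driven by AUC alone, rescue of 10%/3% (placebo/active) gives 78, 30%/11% gives 64, 50%/23% gives 53 and 60%/30% gives 48. Adding noise of SD 100 to the threshold gives 83 at 10% and 73 at 50% placebo rescue. Noise of SD 200 gives about 86 to 87 throughout.

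**The case against.** The strongest reply is that requiring completion and full primary data is a common completer-type PP definition, that ITT leads, and that a supportive analysis pulled towards zero cannot manufacture a positive superiority result. All of that stands, and it limits the weight of the point. It does not make the analysis informative about adherence, which is what the name implies.

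A reader might infer more than the SAP supports:
- **That PP is a second primary result.** Section 8.1 assigns all efficacy analyses to ITT, section 10 adds PP as a further assessment, and no rule requires PP to succeed.
- **That the main harm is PP disagreeing with ITT.** Under 7.1 the ITT LOCF analysis drops most of the same patients, so the two would largely share the distortion. The FCS sensitivity analysis is where a difference could appear.
- **That readings absent after rescue are protocol deviations**, from "Only omitted values will be considered as protocol deviations" in 3.2. That sentence separates mistimed from skipped readings and need not cover readings after the early-discontinuation assessment. In addition, 8.2 excludes only for major violations. The point does not need it.
- **That PP keeps only patients who did well.** It keeps everyone who reached 6 h unrescued, including those who tolerated severe pain. Rescue after the 6 h reading does not exclude.
- **That the loss of effect must be large.** With a weak link between rescue and pain it is about 2 mm·h.

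**Conclusion.** The point holds for the definition of PP. As written, 8.2 and 10.1 exclude compliant patients because of an outcome, and 7.1 prevents the ITT LOCF analysis from offsetting this. The consequence is a supportive analysis that cannot be read as the effect under adherence. It does not by itself overturn the primary conclusion.

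The exclusion follows from the text alone. Its size does not, because it rests on assumed rescue models. The expected PP difference runs from about 60 (48 to 53 at placebo rescue of 60% to 50% driven by pain alone) to about 88, against 90. The bias is towards zero in every model tried. The normal model is rough: it puts Φ(−173/121) = 7.6% of active patients at an impossible negative AUC. The figures are illustrations and not forecasts.

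**What to change.** Before database lock:
1. **Section 8.2.** Define PP as ITT patients without a major protocol violation. State that rescue taken as the plan permits, and VAS readings absent because of it, are not grounds for exclusion.
2. **Section 10.1.** Replace the two sentences that rule out missing PP data and any replacement with one prespecified rule for post-rescue values in AUC0-6h, for example the pre-rescue early-discontinuation score carried to 6 h. Apply it identically in PP and ITT.
3. **Section 7.1 and the last case of Table 7.1.** Amend to match. Otherwise a PP patient could have an AUC that is invalid in the ITT set to which that patient belongs.
4. **Optional.** Keep the present complete-data analysis as a sensitivity analysis labelled as completers.

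The cost is SAP text only, and no clinical procedure changes. The downside is small: PP will contain imputed post-rescue values, and the result will depend on the rule chosen for them.

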8.3 SAFETY POPULATION

The Safety population is defined as all randomized subject who received at least one dose of study medication. The Safety population will therefore be identical to the ITT population if all randomized subject received at least one dose of study medication. The Safety population will be used to present all safety summaries, by actual treatment received.

9. STUDY PATIENTS

9.1 DISPOSITION

Patient distribution will be presented using descriptive statistic by treatment group. Following data will be presented: number of screened patients, number of patients in analysis populations, number of patients completed the study by the protocol and number of discontinued patients with discontinuation reasons.

9.2 DEMOGRAPHICS AND BASELINE CHARACTERISTICS

Demographic data and baseline characteristics will be presented using descriptive statistic for the ITT analysis populations.

Following parameters will be presented at screening:

- Age
- Gender
- Height
- Weight
- BMI
- Race
- Medical history
- Concomitant diseases
- Previous therapy
- Pregnancy test (for females)
- Oral cavity examination (only abnormal parameters)
- Vital signs (only abnormal parameters)

Between groups comparisons will be performed for:

- Age (ANOVA from LME model)
- Gender

¹ Baseline is Day 1 time 0 minutes

Number and percent of patients with previous medications will be presented as a frequency arrays by ATC (3 and 5 levels) and treatment groups.

Current and history diagnoses will be coded by MEDDRA dictionary. Data will be presented by SOC (System Organ Class) and PT (Preferred Term).

Frequencies of CS¹ oral cavity examination abnormalities at Day 1 will be summarized with descriptive statistics (absolute and relative frequencies). Table will show only CS abnormalities. No between group tests are planned.

Frequencies of CS vital signs abnormalities at Day 1 will be summarized with descriptive statistics (absolute and relative frequencies). Table will show only CS abnormalities. No between group tests are planned.

10. EFFICACY AND SAFETY ASSESSMENT

Efficacy parameters will be assessed for the ITT population. Primary efficacy variable also be assessed for the PP population.

10.1 PRIMARY EFFICACY VARIABLE

Primary variable will be the AUC_{0-6h} without or with LOCF of pain intensity profile between time 0 (baseline value of VAS) and 6 hours post-treatment. AUC_{0-6h} analysis will be based on **actual rather than scheduled timings** and will be calculated using the trapezoidal rule:

$$\sum \frac{P_n + P_{n-1}}{2} (t_n - t_{n-1})$$

where, P_n – pain intensity at point n, t_n – time point n.

Treatment AUCs will be compared using ANOVA methodology (simple GLM model). In case of significant covariates discovered during baseline data analysis, such covariates could be added to the ANOVA model (level to stay 0.15). F-test for type III treatment effect will be used for testing the Null hypothesis.

Null hypothesis (H_0) that OKITASK® is no different from Placebo will be rejected and alternative hypothesis (H_1) that OKITASK® is superior to Placebo will be accepted if mean AUC_{0-6h} (OKITASK®) is less than mean AUC_{0-6h} (Placebo) and $p < 0.05$.

$$H_0: \mu_T = \mu_R$$

$$H_1: \mu_T \neq \mu_R$$

where μ_T – OKITASK® (**Test**) mean AUC_{0-6h} ; μ_R – Placebo (**Reference**) mean AUC_{0-6h} .

If the actual time is not recorded, the scheduled time will be used instead. LOCF approach will be applied as described in Section 7.

Additional test on FCS replaced data will be performed to confirm analysis of the LOCF data (sensitivity).

For the PP population data could not be missing. There were no LOCF or other methods applied.

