7. REPLACEMENT OF THE MISSING DATA

7.1 PRIMARY EFFICACY

Considering that the primary variable AUC_{0-6h} is derived from pain intensity VAS measurements, analyses on primary and secondary variables without or with substitution of missing data, using the last observation carry forward (LOCF) methodology, has been considered in order to avoid bias in the inferential testing of treatment effect.

For LOCF analysis substitution of missing data will be applied only on all patients that have at least one VAS value post-baseline (patient compliant with ITT population definition). Missing post-baseline pain score will be replaced with previous one. **Baseline data (pre-dose) could be carried forward also.** Possibility to use baseline data comes from the data nature, which seems to be linearly decreasing over time. This will allow to calculate AUC in case of missing first post-baseline value (5 minutes).

If data be missing more than one time point after baseline, the data will be qualified as invalid. Consecutive missing values will be replaced with the last non-missing (observed) value. If more than two time points data are missing and after missing data some points have values (non-missing), then all missing sequence will be replaced with last non-missing value. In case of absence non-missing values after two missings, no replacement will be done and data will be find invalid for analysis. Possible cases are presented in table below:

¹ Cite from the Study Protocol

² SAS 9.2 <http://support.sas.com/documentation/92/>

Table 7.1 LOCF missing data replacement cases

Time points	Scale	Scale LOCF	AUC
0 (baseline)	A	A	Valid
1	B	B	
2	.	B	
3	.	B	
4	C	C	
5	D	D	
0 (baseline)	A	A	Valid
1	.	A	
2	B	B	
3	C	C	
4	D	D	
5	E	E	
0 (baseline)	A	A	Invalid
1	.	.	
2	.	.	
3	B	B	
4	C	C	
5	D	D	
0 (baseline)	A	A	Valid
1	B	B	
2	.	B	
3	.	B	
4	.	B	
5	C	C	
0 (baseline)	A	A	Invalid
1	B	B	
2	C	C	
3	.	.	
4	.	.	
5	.	.	

For the sensitivity analysis the fully conditional specification (FCS) regression method¹ will be used for replacing missing data.

SAS code example:

```
proc mi data=pain round=1. seed=139592 out=pain_imp;
  class trt;
```

¹ Van Buuren 2007; Brand 1999; Rubin 1987

http://documentation.sas.com/?docsetId=statug&docsetTarget=statug_mi_details07.htm&docsetVersion=14.3&locale=en

² Could be any other

```

fcs nbiter=20 reg (pain=time trt time*trt/details);
var pain time trt;
run;

```

Pain dataset description:

Alphabetic List of Variables and Attributes						

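### Section 10.1 gives the primary AUC0-6h two versions under one superiority rule and does not say which version decides

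*SAP*

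**What the plan says.** Section 10.1 defines the endpoint with two options: "Primary variable will be the AUC_{0-6h} without or with LOCF of pain intensity profile". It then gives a single decision rule: H0 is rejected in favour of superiority if the OKITASK mean AUC is lower than the placebo mean and p is below 0.05. The test is named ("F-test for type III treatment effect will be used for testing the Null hypothesis"); the version of the AUC is not.

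Section 7.1 repeats the pair, referring to "analyses on primary and secondary variables without or with substitution of missing data", and gives avoiding bias in the inferential test as the reason. Section 8.1 sets the population: "The ITT will be used for all efficacy analyses". Section 10 adds PP for this endpoint: "Primary efficacy variable also be assessed for the PP population". Section 10.2 uses the same two-version wording for the pain-relief AUC and restricts secondary variables to ITT.

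Other text leans one way. Section 10.1 says of the imputation analysis: "Additional test on FCS replaced data will be performed to confirm analysis of the LOCF data (sensitivity", and of the PP analysis: "There were no LOCF or other methods applied". Tables 12.9 and 12.11 show ITT with LOCF plus multiple imputation. Tables 12.10 and 12.12 show PP without LOCF. A footnote to Section 12 allows the final tables to differ from these examples.

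On curves that end early, Section 3.2 places the last VAS before rescue dosing. Section 7.1 says that when two missing readings have no observed value after them, nothing is replaced and the data are invalid. The last case in Table 7.1 shows such a terminal gap as invalid.

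**The concern.** A primary analysis should allow one result to decide. Here two AUCs can be computed in the same ITT set and one rule fits both, so the sponsor could read the claim from whichever is significant.

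The two versions can also treat rescued patients very differently. These patients have their VAS curve cut short because their pain was poorly controlled. How they enter the AUC, or whether they enter it at all, can change the estimated effect, and the SAP settles this badly for both versions.

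**Working it through.** **1. The plan's own figure.** Inputs from Section 6: difference 90, SD 121, alpha 0.05, power 80%, 1:1.

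n per arm = 2 × (1.960 + 0.842)² × 121² / 90² = 2 × 7.85 × 14641 / 8100 = 28.4, rounded up to 29, so 58 in total. With 15% drop-out, 29 / 0.85 = 34.1, rounded up to 35, so 70 in total. Both figures reproduce with a two-sided alpha; a one-sided alpha would give 23 per arm. A two-sided 5% test with a direction condition leaves 2.5% for a false superiority claim.

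**2. Does the text confine the no-LOCF version to PP?** Section 8.2 requires PP patients to have all primary assessments, and Section 10.1 says PP data could not be missing. In PP the two versions are therefore the same number, and the option makes a difference only in ITT. Section 10.2 uses the same phrase for a variable analysed only in ITT. The phrase cannot simply be shorthand for the PP analysis.

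**3. Size of the choice.** With two independent tests, 1 − (1 − 0.025)² = 4.9%. Whatever the dependence, the ceiling is 2 × 2.5% = 5%.

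**4. A no-LOCF AUC when VAS stops at rescue.** The SAP states no rule. At a flat 60 mm the full AUC is 60 × 6 = 360 mm·h. If the trapezoid is summed over observed points only, rescue at 1 h gives 60 × 1 = 60, at 2 h gives 120 and at 4 h gives 240. If the AUC is instead treated as missing, the patient is dropped.

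**5. The LOCF AUC under Section 7.1.** The last scheduled readings are at 4, 5 and 6 h. A patient rescued before the 5 h reading misses both 5 h and 6 h, so the AUC is invalid. Only a patient who loses just the 6 h reading keeps one.

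**6. Simulation.** All patient-level inputs are assumptions: 35 per arm; patient mean pain centred on 263/6 or 173/6 mm with SD 19; reading-to-reading SD 10; baseline about 55 mm; rescue possible at scheduled readings from 1 to 5 h when pain exceeds 50 mm, with probability 0.05, 0.15 or 0.40 per reading. There were 1500 trials with an effect and 3000 without. Differences are placebo minus active in mm·h, with power in brackets.

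| Rescue, placebo/active | Invalid under Table 7.1 | Summed to last observed point | Table 7.1 LOCF | Last value carried to 6 h for all | Full data |
|---|---|---|---|---|---|
| 11% / 5% | 9% / 4% | 70 (78%) | 80 (85%) | 84 (89%) | 84 (89%) |
| 27% / 12% | 23% / 10% | 50 (56%) | 72 (77%) | 86 (89%) | 85 (90%) |
| 48% / 23% | 44% / 21% | 20 (17%) | 52 (51%) | 87 (88%) | 84 (89%) |

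With no true effect and equal rescue of 11%, 27% and 48% in both arms, each of the first two versions alone gave a false superiority claim in 2.3-2.8% of trials. Allowing either the summed version or Table 7.1 LOCF to decide gave 3.2%, 3.9% and 4.1%.

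The simulated profiles are flat after dosing, which suits carrying forward. The carried-to-6 h column is therefore not evidence that LOCF is unbiased in real data.

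**The case against.** The strongest reply is that the intended analysis can be recognised. Section 10.1 says LOCF will be applied as in Section 7 and makes the FCS test a confirmation of the LOCF result. No shell shows ITT without LOCF. On this reading, *without* belongs to PP and *with* to ITT. Much of this stands: LOCF in ITT is the likelier intention, and the choice is not wide open. But no sentence says so, the shells are declared changeable, and Section 10.2 uses the phrase for an ITT-only variable.

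A reader might infer that the plan scores rescued patients on a truncated AUC. The documents do not say that. The variable is defined up to 6 h, and Section 7.1 calls data with a terminal gap invalid, so treating such an AUC as missing is as natural a reading. On that reading the two versions would differ little for rescued patients, and the gain from choosing between them would be smaller than simulated.

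A reader might also infer that truncation would help the drug. If rescue is commoner on placebo, it works against the drug, as the table shows. With equal rescue, the truncated version alone kept its error rate near 2.5%; the inflation comes from having two versions to choose from.

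Finally, a reader might take LOCF as the safe version because carrying forward kept the difference at 84-87 mm·h. Table 7.1 does not carry forward in that way for most rescued patients, so that stability is not a property of this SAP.

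**Conclusion.** The point holds as a defect of specification that should be corrected before unblinding. One superiority rule covers two versions of the primary AUC and no sentence names the one that decides.

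The error cost is moderate. The false superiority rate is 4.9% instead of 2.5% if the tests were independent. It was 3.2-4.1% in simulation with the Table 7.1 rule, which rests on assumed rescue rates and on summing the no-LOCF curve to its last observed point.

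Naming LOCF alone would not be enough. Under Section 7.1 most rescued patients lose their AUC. In the simulated settings this lowered the difference from about 84 to 80, 72 and 52 mm·h as rescue increased. Neither version now gives rescued patients a defined AUC over the full window.

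**What to change.** - **Section 10.1:** delete *without or*. State that the single test of H0 is the ITT comparison of AUC0-6h under one named missing-data rule (the LOCF row of Table 12.9, if that is the intention). State that the PP and FCS analyses are supportive and cannot by themselves reject H0.
- **Section 7.1 and Table 7.1, in the same step:** amend the rule so that every ITT patient whose VAS ends early has an AUC over the full 0-6 h window. One example is to carry the last pre-rescue value to 6 h, with the FCS imputation as sensitivity analysis. State that sums over part of the window are not used as AUC0-6h.
- **Section 10.2:** make the same change for the pain-relief AUC.

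The cost is SAP wording only. The sponsor gives up the choice between versions, and the sample size stays at 58 before and 70 after drop-out.
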